## 2.3 Secondary Objectives and Endpoints

Secondary Objectives	Endpoints	Time Frame
1. To determine the rate of grade $\geq 2$ hearing impairment based on CTCAE version 5 with use of STS after concurrent chemoradiation with cisplatin 3 months post-treatment	Incidence of ototoxicity defined by of grade $\geq 2$ hearing impairments based on NCI CTCAE version 5.0 (for patients on a monitoring program) with audiogram in each cohort	3 months after completion of chemoradiation
2. To determine the rate of tinnitus measured by PRO-CTCAE with use of STS 3 months post-treatment	
 
Incidence of tinnitus using PRO-CTCAE in each cohort
 
	3 months after completion of chemoradiation
3. To describe patient reported outcomes with STS measured with PRO-CTCAE for selected oral, GI, neurologic and perceptual symptoms	
 
Description of incidence and trend of patient reported outcomes using PRO-CTCAE in each cohort
 
	3 months after completion of chemoradiation
4. To describe patient reported outcomes measured with Hearing Handicap Inventory for Adults – Screening (HHIA-S) compared to results from standard NRG Oncology head and neck trials (such as RTOG 1016)	
 
Description of incidence and trend of patient reported outcomes using HHIA-S in each cohort
 
	3 months after completion of chemoradiation

## 3 Study Design

### 3.1 Characteristics

This is a phase II study to determine feasibility of STS infused 4 hours after each dose of either weekly or every-3-week cisplatin in SCCHN patients undergoing definitive concurrent chemoradiation with cisplatin. Patients with locally advanced SCCHN (oral cavity, oropharynx, hypopharynx, and larynx) eligible for definitive concurrent chemoradiation with cisplatin would be eligible for the study.

### 3.2 Sample Size

Target accrual is a total of 16 patients, and to account for screen failures and withdrawals, we will consent up to 18 patients. Patients can be enrolled to the and can get concurrent chemoradiation with weekly cisplatin (40 mg/m^2) given once a week or concurrent chemoradiation with high dose cisplatin (80-100 mg/m^2) given every 3 weeks. Participants who do not receive any dose of STS will not be evaluable and will be replaced.

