## 2 Study Objectives

### 2.1 Hypothesis

We hypothesize that use of intravenous STS would be feasible in patients with locally advanced SCCHN undergoing concurrent chemoradiation with cisplatin.

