### 2.2 Primary Objective and Endpoint

Primary Objective	Endpoint	Time Frame
To establish feasibility of intravenous STS after each dose of concurrent cisplatin in patients with locally advanced head and neck squamous cell carcinoma undergoing definitive radiotherapy.	Feasibility measured by successful completion of planned treatment, defined by completion of at least 5 weekly cisplatin or 2 high dose cisplatin administrations without extended treatment related delays more than 7 days.	Occurring up to 7 days after the last dose of STS

[figure not shown]

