**Table 5.1      Regimen Description**

Investigational Product	Premedication; precautions	Dose	Route	Schedule	Cycle Length
Cisplatin (weekly)	
 
Cisplatin can be given within 24 hours of radiation therapy. If radiation is held for more than 2 days (for any reason), cisplatin may be held as well until radiation resumes.
 
Prophylactic anti-emetic regimen will be given as per UCSF guidelines.
 
1 liter of isotonic fluid will be given intravenously prior to cisplatin infusion
 
	40 mg/m 	Intravenously	Days 1, 8, 15, 22, 29, 36, and 43	
Cisplatin (every-3-weeks)	
 
Cisplatin can be given within 24 hours of radiation therapy. If radiation is held for more than 2 days (for any reason), cisplatin may be held as well until radiation resumes.
 
Prophylactic anti-emetic regimen will be given as per UCSF guidelines.
 
1 liter of isotonic fluid will be given intravenously prior to cisplatin infusion
 
	80-100 mg/m 	Intravenously	Days 1, 22, and 43	Weekly or every 3 weeks
*Sodium Thiosulfate (weekly)	No contraindications	10 g/m 	Intravenously using a Mediport or a PICC line	Between 4-5 hours after each cisplatin infusion sodium thiosulfate will be	

				administered over 1-2 hours	
*Sodium Thiosulfate (every-3-week)	No contraindications	20 g/m 	Intravenously using a Mediport or a PICC line	Between 4-5 hours after each cisplatin infusion sodium thiosulfate will be administered over 1-2 hours	

\*Missed doses of sodium thiosulfate will not be replaced.

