## **8 Statistical Considerations and Analysis Plan**

Feasibility will be evaluated as the successful completion of 5 weekly cisplatin or 2 every-3-week cisplatin without any extended treatment related delays more than 7 days by at least 75% of patients. Safety will be measured by:

- Frequency of drug related adverse events occurring up to 7 days after the last dose of STS
- Frequency of serious adverse events occurring up to 7 days after the last dose of STS
- Frequency of clinical laboratory test abnormalities by worst toxicity grade using NCI CTCAE version 5.0

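### Section 3.2 replaces every participant who never receives STS, including those who have started on-study cisplatin, so complete non-delivery of STS drops out of the primary feasibility rate

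*Combined protocol and SAP*

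**What the plan says.** The hypothesis in Section 2.1 is that "use of intravenous STS would be feasible in patients with locally advanced SCCHN undergoing concurrent chemoradiation with cisplatin". The primary objective in Section 2.2 is "To establish feasibility of intravenous STS after each dose of concurrent cisplatin in patients with locally advanced head and neck squamous cell carcinoma". The endpoint attached to it is counted in cisplatin doses: "completion of at least 5 weekly cisplatin or 2 high dose cisplatin administrations without extended treatment related delays more than 7 days". Section 8 repeats that definition and sets the bar: "without any extended treatment related delays more than 7 days by at least 75% of patients".

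Table 5.1 places STS after cisplatin ("Between 4-5 hours after each cisplatin infusion sodium thiosulfate will be" given over 1-2 hours), through a Mediport or PICC line. Section 5.1 makes treatment outpatient. A footnote to the table says that missed STS doses are not made up.

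On who is counted, Section 3.2 says: "Target accrual is a total of 16 patients, and to account for screen failures and withdrawals, we will consent up to 18 patients". It then adds: "Participants who do not receive any dose of STS will not be evaluable and will be replaced". Sections 7.1.1 and 7.1.2 separately define the toxicity and safety sets by receipt of STS. Sections 8 and 8.4 define no feasibility set of their own and plan no sensitivity analysis that would bring replaced participants back.

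**The concern.** STS follows cisplatin by several hours, so a participant can start study treatment and never receive STS. Acute toxicity, failure of the line, refusal of the extra hours or early withdrawal could each lead to this. Measured against the stated objective, such a participant is a case in which STS could not be delivered at all. Section 3.2 takes that person out of the count and brings in someone else, who is counted only if STS was given at least once.

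Receipt of STS happens after treatment starts and is part of what feasibility means here. Using it to choose the denominator makes the primary rate conditional on at least partial delivery. With a 75% criterion and 16 patients, one person can decide whether the criterion is met. Section 1.3 says the result is meant to support a larger study.

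**Working it through.** **Inputs from the documents.** Target 16 evaluable and at most 18 consented (Section 3.2). Success criterion: at least 75% of patients (Section 8). The share of cisplatin starters who never receive STS is not given anywhere, so it is treated below as an assumption.

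**The plan's own threshold.** 0.75 × 16 = 12, so 12/16 just meets the criterion. With 17 in the denominator, 0.75 × 17 = 12.75, so 13 successes are needed. With 18, 0.75 × 18 = 13.5, so 14 are needed.

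**Upper limit on replacements.** 18 − 16 = 2. Reaching two would require that neither spare consent is used for a screen failure or for a withdrawal before cisplatin.

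**Restoring the replaced starters.** With s successes among the 16 evaluable and k restored participants, the rate is s/(16 + k) if all k are failures, and (s + k)/(16 + k) if all k are successes.

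| s among 16 | k | restored as failures | restored as successes |
|---|---|---|---|
| 12 (75.0%, met) | 1 | 12/17 = 70.6%, not met | 13/17 = 76.5%, met |
| 12 | 2 | 12/18 = 66.7%, not met | 14/18 = 77.8%, met |
| 13 (81.3%, met) | 1 | 13/17 = 76.5%, met | 14/17 = 82.4%, met |
| 13 | 2 | 13/18 = 72.2%, not met | 15/18 = 83.3%, met |
| 14 (87.5%, met) | 2 | 14/18 = 77.8%, met | 16/18 = 88.9%, met |

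When restored participants are failures, the conclusion reverses at 12 successes with one restored, and at 12 or 13 with two. From 12/16, the rate falls by 75.0 − 70.6 = 4.4 points or 75.0 − 66.7 = 8.3 points.

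**Which column applies.** The endpoint in Section 2.2 requires cisplatin completion without a long delay and requires no STS dose. A never-STS participant who withdraws after Day 1 has not completed cisplatin and belongs in the failure column. One who completes cisplatin on time belongs in the success column under the present text, and moves to the failure column only if non-delivery is expressly scored as failure.

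**Illustration with an assumed rate.** Let q be the share of starters who never receive STS, scored as failures, and assume 75% success among STS recipients. The all-starters rate is (1 − q) × 0.75. The chance of at least 12 successes in 16 in the evaluable set is 63.0% whatever q is. Among 16 consecutive starters it is lower:

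| q (assumed) | all-starters rate | chance of ≥12/16 |
|---|---|---|
| 5% | 71.3% | 49.4% |
| 10% | 67.5% | 36.6% |
| 12.5% | 65.6% | 30.7% |

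**Precision.** Exact 95% intervals are 47.6-92.7% for 12/16, 44.0-89.7% for 12/17 and 41.0-86.7% for 12/18. The 0.345 margin in Section 8.2 does not reproduce at n = 16 (1.96 × √(0.5 × 0.5/16) = 0.245), but nothing here uses it.

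**The case against.** The best defence is that the written endpoint asks whether cisplatin can be completed when STS is given. A participant never exposed to STS cannot inform that question, and a treated set matches the safety set. On that reading a never-STS patient is not automatically a failure, and the 12/17 and 12/18 figures assume a scoring that the plan does not contain. This stands as a limit on the direction of the bias. It does not rescue the rule, because the stated objective is delivery of STS after each cisplatin dose, and under Section 3.2 total non-delivery appears nowhere in the primary result.

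The affected group is also small. Exclusion criterion 6 removes people without secure venous access, criterion 2 removes some likely non-compliers, and the spare consents have other uses. Zero such patients is possible. Section 8.2 claims only preliminary evidence, Section 8.4 only describes feasibility, and the exact intervals overlap almost entirely. All of this stands and lowers the severity.

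A reader might infer that anyone who receives Day 1 cisplatin and misses that day's STS is dropped. The documents do not support this. The rule applies only when no STS is received over the whole course. Table 5.1 foresees missed doses, and a participant who misses one STS dose but receives a later one stays evaluable.

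**Conclusion.** The concern holds, within limits. Section 3.2 removes complete non-delivery of STS among cisplatin starters from the primary rate of an STS feasibility trial, and nothing elsewhere restores it. Replacing participants who never start on-study cisplatin is reasonable and is not in question.

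The effect is at most two patients. It is upward if those patients also fail cisplatin completion, or if non-delivery is scored as failure; one is then enough to turn a 12/16 result from met to not met. A reader might go further and conclude that the rule necessarily inflates the rate. The documents do not support that: under the cisplatin-only endpoint, adding back a never-STS completer raises 12/16 to 13/17. The number of such patients (0 to 2) is an assumption. Because of the small numbers and the descriptive analysis, this should be fixed but is not critical.

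**What to change.** In Sections 3.2 and 8, define the feasibility set as all registered participants who receive a first on-study cisplatin dose with STS planned, and replace only those who never start on-study cisplatin.

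In Sections 2.2 and 8, add that a participant in this set who receives no STS at any dose counts as a feasibility failure. Present this as a change of endpoint, since the current definition requires no STS dose; changing the denominator alone would still score a never-STS cisplatin completer as a success. Report the number of such participants and the reasons. Leave the safety set in Section 7.1.2 (at least one STS dose) as it is.

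The cost is a few sentences. It needs no extra patients and no new data, because the study calendar already lists cisplatin and STS administration. The downside is that the feasibility percentage may be slightly less favourable. The change does not settle how partial STS delivery should be scored: a participant with one STS dose and cisplatin completed on time would still be a success. That is a separate question about the endpoint.

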### 3.3 Eligibility Criteria

#### 3.3.1 Inclusion Criteria

1. Participants must have histologically or cytologically confirmed locoregionally advanced squamous cell carcinomas of mucosal surfaces of head and neck who are being treated with concurrent chemoradiation with cisplatin.
2. Participants must be eligible for cisplatin-based concurrent chemotherapy in conjunction with at least 6 weeks of daily fractionated radiation therapy.
3. Age  $\geq 18$  years
4. ECOG performance status  $\leq 2$  (Karnofsky  $\geq 50\%$ , see Appendix 1)
5. Demonstrates adequate organ function as defined below:

Adequate bone marrow function:

absolute neutrophil count	≥1,000/mcL
platelets	≥100,000/mcL
Adequate hepatic function:	
total bilirubin	within normal institutional limits, unless elevated due to Gilbert's syndrome and direct bilirubin is within normal limits
AST(SGOT)	≤3 X institutional upper limit of normal
ALT(SGPT)	≤3 X institutional upper limit of normal
Adequate renal function:	
creatinine	≤ 1.5 x within institutional upper limit of normal
OR	
creatinine clearance	GFR ≥ 60 mL/min/1.73 m  , calculated using the Cockcroft-Gault equation, unless data exists supporting safe use at lower kidney function values, no lower than 30 mL/min/1.73 m 

6. Ability to understand a written informed consent document, and the willingness to sign it
7. Individuals with a prior or concurrent malignancy whose natural history or treatment does not have the potential to interfere with the safety or efficacy assessment of the investigational regimen are eligible for this trial.
8. The effects of sodium thiosulfate (STS) on the developing human fetus are unknown. For this reason and because cisplatin used in this trial are known to be teratogenic, women of child-bearing potential and men must agree to use adequate contraception such as hormonal and/or barrier method of birth control for the duration of study participation and for 3 months after last administration of study treatment. Should a woman become pregnant or suspect she is pregnant while she or her partner is participating in this study, she should inform her treating physician immediately.

Men treated or enrolled on this protocol must also agree to use adequate contraception prior to the study, for the duration of study participation, and 3 months after last administration of study treatment.

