### 3.3.2 Exclusion Criteria

1. Participants that are not eligible for cisplatin-based chemoradiation for reasons such as chronic kidney disease, severe hearing loss, and severe peripheral neuropathy.
2. Uncontrolled inter-current illness or psychiatric illness/social situation that would limit compliance with study requirements
3. Has known hypersensitivity to cisplatin, sodium thiosulfate or any of its excipients.
4. Has profound hearing impairment at baseline and cannot hear a sound below 90 dB
5. Participants with uncompensated congestive heart failure NYHA class 3 or above.

6. Participants who cannot get secure venous access using either a Mediport or a PICC line for safe administration of intravenous sodium thiosulfate.
7. Pregnant women are excluded from this study because cisplatin is a cytotoxic agent with the potential for teratogenic or abortifacient effects. Because there is an unknown but potential risk for adverse events in nursing infants secondary to treatment of the mother with cisplatin or sodium thiosulfate, breastfeeding should be discontinued if the mother is treated with either agent.

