### 5.2.3 Renal Adverse Events:

Cisplatin dose should be based on the serum creatinine or creatinine clearance immediately prior to the second cisplatin dose using the following guidelines:

Note: If creatinine is > 1.5 mg/dl, creatinine clearance must be calculated (Cockcroft-Gault) in order to make dose adjustment. The cisplatin dose will be determined as follows:

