#### Serum Creatinine Clearance Cisplatin Dose

- $\leq$  1.5 mg/dl or > 50 ml/min full dose
- 1.5 mg/dl and < 50 ml/min Hold drug\*

\*Cisplatin should be held (but the RT continued) and the creatinine measured weekly, until it is

- < 1.5 mg/dl or the creatinine clearance is > 50 ml/min, and then the second dose of cisplatin can be given at the reduced dose by 50%.

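### Inclusion 5 and section 5.2.3 set inconsistent renal limits for cisplatin, and section 5.2.3 is worded for the second dose only

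*Combined protocol and SAP*

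**What the plan says.** **Entry.** Section 3.3.1, inclusion 5, defines adequate renal function by either of two routes joined by OR. The first is creatinine "≤ 1.5 x within institutional upper limit of normal". The second is a Cockcroft-Gault clearance of at least 60 mL/min/1.73 m², "unless data exists supporting safe use at lower kidney function values, no lower than 30 mL/min/1.73 m"². A patient who meets the creatinine route needs no clearance value.

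**Dosing.** Section 5.2.3 bases the cisplatin dose on renal function "immediately prior to the second cisplatin dose using the following guidelines". Above 1.5 mg/dl, "creatinine clearance must be calculated (Cockcroft-Gault) in order to make dose adjustment". Full dose is given if creatinine is at most 1.5 mg/dl or clearance is above 50 ml/min. The hold line reads "1.5 mg/dl and < 50 ml/min Hold drug"; the note above it shows that creatinine greater than 1.5 mg/dl is meant. After recovery, "then the second dose of cisplatin can be given at the reduced dose by 50" per cent.

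**General safeguards.** Inclusion 2 says "Participants must be eligible for cisplatin-based concurrent chemotherapy in conjunction with" radiotherapy. Exclusion 1 removes patients "not eligible for cisplatin-based chemoradiation for reasons such as chronic kidney disease". Section 4.1.2 lists pre-existing renal impairment as a contraindication to cisplatin. Section 3.5 stops treatment if an exclusion criterion emerges or is recognised late. None of these gives a creatinine or clearance value.

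**Measurement.** Screening may be up to 28 days before the first dose (section 6). Chemistry, including creatinine, is drawn on day 1 and on each later treatment day (sections 6.1 and 6.3.2).

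**The concern.** Entry uses a limit relative to the laboratory's ULN, or a clearance that may go down to 30. The hold rule uses an absolute creatinine limit combined with a clearance of 50 ml/min. Unless the two are aligned, the numeric criteria can label as adequate a renal function that the same protocol treats as too poor for dosing. Because the hold rule is tied to the second dose, its wording does not catch such a patient on day 1, even though the creatinine result is requested that day.

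What is at stake is patient safety at the first dose, which may be up to 100 mg/m² of a nephrotoxic drug. Read literally, the same wording leaves weekly doses 3 to 7, and a third every-3-week dose, without a renal action limit.

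**Working it through.** The plan gives no figure on this point to reproduce. The check compares the limits and then applies the equation that the protocol names.

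**Inputs from the documents.** Entry limits are from inclusion 5, with the creatinine route read as 1.5 × ULN (the phrase is garbled, but this is the likeliest reading). The hold condition is from section 5.2.3: creatinine above 1.5 mg/dl and clearance below 50 ml/min.

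**Assumptions.** ULN, age, weight, sex and body surface area are not given, so the values below are illustrative.

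**Step 1: creatinine route.** 1.5 × ULN exceeds 1.5 mg/dl exactly when ULN exceeds 1.0 mg/dl. At a ULN of 1.0 or less, nobody entering by this route meets the hold condition at the entry value.

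**Step 2: who falls in the overlap.** Clearance = (140 − age) × kg / (72 × creatinine), × 0.85 for women.

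- Man, 65 years, 70 kg, creatinine 1.6: 75 × 70 / (72 × 1.6) = 45.6 ml/min. He enters if ULN is at least 1.6 / 1.5 = 1.07, and he meets the hold condition.
- Same man at 90 kg: 75 × 90 / (72 × 1.6) = 58.6 ml/min. He is not held.

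For a man exactly at the entry limit (the worst case), clearance is below 50 when age exceeds 140 − 50 × 72 × creatinine / kg:

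| Assumed ULN (mg/dl) | Entry limit (mg/dl) | 60 kg | 70 kg | 80 kg | 90 kg |
|---|---|---|---|---|---|
| 1.0 | 1.50 | no overlap | no overlap | no overlap | no overlap |
| 1.1 | 1.65 | 41 y | 55 y | 66 y | 74 y |
| 1.2 | 1.80 | 32 y | 47 y | 59 y | 68 y |
| 1.3 | 1.95 | 23 y | 40 y | 52 y | 62 y |

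The table shows which patients could be affected. It does not show how many.

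**Step 3: clearance route.** This does not depend on the ULN. Take ULN 1.0 and a man of 70 years, 70 kg, creatinine 1.8. He fails the creatinine route (limit 1.50). His clearance is 70 × 70 / (72 × 1.8) = 37.8 ml/min. At an assumed body surface area of 1.73 m², that is also 37.8 mL/min/1.73 m², inside the 30 to 60 range that the exception opens. If the exception is invoked, he enters while meeting the hold condition. The documents do not say which data support the exception or who decides.

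**Step 4: timing.** Creatinine is requested on day 1, but section 5.2.3 names only the second dose, both for the check and for the restart. No other section gives a renal action limit for dose 1.

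**Step 5: units.** Entry uses mL/min/1.73 m² and section 5.2.3 uses ml/min. The two agree only at a body surface area of 1.73 m². This is a minor point.

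**Step 6: after the fix.** If clearance must be above 50 ml/min whenever creatinine exceeds 1.5 mg/dl, every admitted patient has creatinine of at most 1.5 mg/dl or clearance above 50 ml/min. That is the full-dose condition of section 5.2.3, so the overlap is empty at any ULN.

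**The case against.** The strongest reply is that inclusion 5 is necessary, not sufficient. A patient with creatinine above 1.5 mg/dl and clearance below 50 ml/min before treatment is the kind of patient whom inclusion 2, exclusion 1 and the contraindication in section 4.1.2 are meant to keep out. This stands as a reason for low frequency and low severity. It does not remove the inconsistency, because those provisions give no number while inclusion 5 supplies the protocol's own numeric definition of adequate function.

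Second, the ULN is not stated, so an overlap on the creatinine route cannot be shown for this site. That also stands, and the claim for that route is conditional. The exception down to 30 does not need it.

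Third, the second-dose wording may be loose drafting. Sections 5.2.1 and 5.2.2 use it too, and a literal reading would leave most weekly doses unchecked, which is unlikely to be intended. This is probably right, and it is a reason to correct the words.

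Fourth, the fix leaves worse renal function untouched. A woman of 75 years and 50 kg with creatinine 1.4 mg/dl has clearance 65 × 50 × 0.85 / (72 × 1.4) = 27.4 ml/min. She can still enter if ULN is at least 1.4 / 1.5 = 0.93, and section 5.2.3 would give full dose. This is true. In her case the two sections agree with each other, and where to set a clearance floor is a separate clinical question that still relies on exclusion 1.

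**Conclusion.** The inconsistency is real and of low severity. The clearance exception can admit a patient who already meets the hold condition, and the creatinine route can do so if the ULN exceeds 1.0 mg/dl. As worded, section 5.2.3 sets no numeric limit for dose 1. The frequency cannot be estimated from the documents and is expected to be low.

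Two stronger readings should be resisted. A reader might infer that the protocol directs cisplatin to patients with renal impairment. It does not: read as a whole, it excludes them by judgement and lacks only a consistent number.

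A reader might also infer that the mismatch threatens the feasibility endpoint or the stopping rule. That is remote:

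- An every-3-week patient whose second dose is never given, and who is not switched to weekly cisplatin under section 5.2.5, would miss the two administrations required in section 2.2 and count toward Table 1 in section 5.4.
- A half-dose restart still counts as an administration. From 100 mg/m², a third dose at full or half strength gives 100 + 50 + 100 = 250 or 100 + 50 + 50 = 200. From 80 mg/m², it gives 80 + 40 + 80 = 200 or 80 + 40 + 40 = 160. Three of these four paths reach 200 mg/m².
- A switch followed by three weekly doses gives 100 + 3 × 40 = 220 or 80 + 3 × 40 = 200. Section 5.2.5 does not say whether it overrides a continuing renal hold.
- Section 2.2 counts only treatment-related delays, so a delay alone may not be a failure.
- One such patient cannot stop a stratum. With the Beta(2, 6) prior, one failure in one patient gives Beta(3, 6) and a posterior probability of 0.679 that the rate exceeds 25%, below the 0.70 threshold. One failure in four gives Beta(3, 9) and 0.455.

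The case for change rests on consistency and first-dose safety, not on the trial's operating characteristics.

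**What to change.** In section 5.2.3, make the renal check apply immediately before each cisplatin dose, including the first, and reword the restart line to match. The clinical team should decide whether the 50% restart applies to a held first dose.

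In inclusion 5, keep both routes but add that, by either route, Cockcroft-Gault clearance must be above 50 ml/min whenever creatinine exceeds 1.5 mg/dl. Delete the exception down to 30, or limit it to values above 50. State clearance in ml/min in both sections.

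The cost is a text amendment and slightly narrower eligibility. No tests are added, because creatinine is already measured at screening and on every treatment day. The change aligns entry with the hold rule only; it sets no clearance floor for creatinine of 1.5 mg/dl or less.
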